5.1.1.1.2 Relative day

Relative day will be derived with the date of treatment in each Period (treatment and washout) as reference for that specific Period.

- Relative Day 1 is the date of treatment.

- For days prior to first treatment:

Relative day = Current date – Date of first treatment.

- For days after the day of treatment in Period:

Relative day = Current date - Date of treatment within the same Dosing Period +1.

- For days after the day of last treatment:

Relative day = Current date - Date of last treatment +1.

There is no Relative day 0. Relative day will not be calculated for partial dates. Relative day for partial days will be displayed as ‘--’ to distinguish it from missing values which are displayed as blanks.

5.1.1.1.3 End date of the Treatment Period

Treatment periods are specified in Section 5.1.1.1.4.

5.1.1.4 Study Periods

The maximum study duration will be 48 days, including the Treatment Period and the Safety Follow-Up (SFU) Period. There are 3 study periods in this study:

- Screening Period: Eligibility will be assessed during the Screening Period (up to 28 days). Treatment must be started as soon as possible for participants who have fulfilled the eligibility criteria.
- Treatment Period: Participants who have been confirmed eligible will be randomized to receive open-label single doses of minzasolmin [REDACTED] on Days 1, 6, and 11 with a 4-day Washout Period between doses.
- Safety Follow-Up Period: Study participants will have SFU procedures performed within 5 to 9 days after final dose. Participants who prematurely withdraw from the study will return to the clinic center for the Early Termination Visit (ETV) as soon as possible after the time of withdrawal and will have all SFU procedures performed.

Table 4 Study Periods and Durations

Period	Study Day	Duration	Relative Day
Screening Period	Study Day -28 to -2	Day -28 to Day -2	Relative Day -28 to -2
Treatment Period 1	Study Day -1 to 1	Day -1 to Day 1	Relative Day -1 to 1
Washout Period 1	Study Day +2 to +5	Day 2 to Day 5	Relative Day +2 to +5
Treatment Period 2	Study Day 6	Day 6	Relative Day 1
Washout Period 2	Study Day 7 to Day 10	Day 7 to Day 10	Relative Day +2 to +5
Treatment Period 3	Study Day 11	Day 11	Relative Day 1
Washout Period 3	Study Day 12 to Day 15	Day 12 to Day 15	Relative Day +2 to +5
Safety Follow-Up	Study Day 16 to 20	Day 16 to 20	Relative Day +6 to +10

5.1.1.5 Mapping of assessments performed at Early Termination Visit

Safety assessments made at an early termination visit that correspond to a scheduled visit will be summarized at the scheduled visit to correspond to the early termination visit if the assessment was scheduled to occur at that visit. Such assessments at the early termination visit will also be considered for safety follow up/ termination visit.

5.1.1.6 Definition of Baseline values

Unless otherwise stated, a Baseline value refers to the last non-missing value collected prior to the first treatment. Scheduled or unscheduled measurements can be used as the Baseline value. If a Baseline measurement is repeated and is obtained prior to the first treatment, then the last available measurement will be used as the Baseline value. If an unscheduled measurement occurs after the planned Baseline measurement time point but before the first treatment, then the unscheduled measurement will be used.

Table 5 Definition of Baseline

Procedure	Baseline Day
Vital sign	Predose on Day 1 or if missing then the Baseline data will be missing.
Single 12-lead ECG	
Laboratory assessments (hematology, clinical chemistry, and urinalysis)	Baseline is defined as the value on Day -1. If this value is missing, the most recent value obtained prior to Day 1 will be used as Baseline.

ECG= electrocardiogram

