^b Study participants will have SFU procedures performed within 5 to 9 days after final dose. Participants who prematurely withdraw from the study will return to the clinic center for the ETV as soon as possible after the time of withdrawal and will have all SFU procedures performed.

^c Clinical assessments performed on Days 1, 6, and 11 need to be performed predose.

^d Complete physical examinations will be performed during Screening, at Day -1, and at SFU/ETV. Symptom-directed physical examinations will be performed during Treatment Periods.

^e Blood hematology and chemistry laboratory tests will be obtained in the fasting state following an overnight fast of at least 10 hours. Hepatic function tests only will also be performed 24 hours before each dosing (ie, Day 5 and Day 10). Note that FSH and estradiol will only be determined for females at the Screening Visit.

^f 12-lead ECG will be performed in single after a rest in supine position for at least 10 minutes before recordings, but can be repeated in triplicate if clinically indicated.

^g SBP, DBP, respiration rate, PR, and body temperature. Vital signs will be performed after a rest of at least 5 minutes.

^h The PK sampling timepoints will be: predose and at 0.5, 1, 1.5, 2, 4, 8, 12, 24, 36, 48, 72, and 96h after minzasolmin administration on Day 1, Day 6, and Day 11.

ⁱ Study participants will receive standard meals and snacks at appropriate times indicated by the clinic center, except when they are required to fast. All participants fast overnight for at least 10 hours before minzasolmin administration. Participants in Treatment A and B continue fasting for at least 4 hours after minzasolmin administration. Thereafter they receive a standard lunch. Fed study participants (Treatment C) should start the recommended high-fat high-calorie meal 30 minutes before administration of minzasolmin. Study participants should eat this meal in 30 minutes or less; however, minzasolmin should be administered 30 minutes after start of the meal. No food should be allowed for at least 4 hours postdose. During the rest of the day, study participants receive standard meals and snacks at appropriate times indicated by the clinic center.

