4.2 Scientific rationale for study design

A new tablet formulation is developed for minzasolmin, which is planned to be used in future studies and for commercialization purpose. The current study UP0152 is designed to evaluate the relative bioavailability of a new tablet formulation compared with the current clinical formulation (ie, granules in capsule) under fasting condition. In addition, the study is also designed to evaluate the potential effect of a high-fat meal on the PK of minzasolmin when administered as tablet formulation. A crossover study design was selected as it provides more robust comparison between different formulations and fed conditions as each participant will receive all study treatments. Six sequences were implemented in order to balance the allocation of treatments across study periods.

The half-life of minzasolmin and its 2 metabolites (████████) are 11, 10 and 16 hours, respectively (see the IB for further details). Considering 5 half-lives for elimination of the drug, the 4 days washout is considered adequate for the study. In study UP0073, a similar design and washout period was used, and carryover (<5% of C_{max}) was observed in only few participants. The t_{max} for minzasolmin and the ██████████ metabolites were 1.5, 2.0, and 2.0 hours, respectively (see the IB for further details).

UP0152 will provide safety, tolerability, and PK information of minzasolmin formulations in fed condition (tablet formulation) and fasting condition (tablet and ‘granules in capsule’ formulation) after single oral doses of minzasolmin ██████████ administered once per period in healthy study participants.

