7.1.2 Corrected QT interval stopping criteria

A participant who meets either bulleted criterion based on single 12-lead ECG readings will be withdrawn from the study. If there are abnormalities that are considered clinically significant for a particular study participant, ECG recordings will be performed in triplicate at 2- to 3-minute intervals (3 ECGs within a 5-minute timeframe) before the exclusion of the participant.

- QTcF >500ms OR Uncorrected QT >600ms
- Change from Baseline (Day -1, before first treatment, Day 6, and Day 11) of QTcF >60ms

If a clinically significant finding is identified (including, but not limited to, changes from Baseline in QTcF after enrollment, the investigator or qualified designee will determine if the participant can continue on the study intervention and if any change in participant management is needed. This review of the ECG printed at the time of collection must be documented. Any new clinically significant finding should be reported as an AE.

See the Schedule of Activities (Section 1.3) for data to be collected at the time of intervention, discontinuation and follow up and for any further evaluations that need to be completed.

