9.2.4.1 Exploratory safety endpoints analysis

Laboratory variables and changes from Baseline (Day -1, or Day 1 before first treatment) will be summarized by time point and will be presented by treatment group. For categorized values according to the reference range, shift tables from Baseline to each post-Baseline time point will be presented for selected variables to be defined in the SAP. Values outside the reference range will be flagged in the listings.

Vital sign variables (SBP, DBP, PR, respiration rate, and body temperature) and changes from Baseline (Day -1, or Day 1 before first treatment) will be summarized by time point and will be presented by treatment group.

The single 12-lead ECG will be recorded as timepoints defined in schedule of activities.

Descriptive statistics will be presented for ECG values and changes from Baseline (Day -1, before first treatment, Day 6, and Day 11) through treatment periods.

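### SAP Table 5, on its most likely reading, ties ECG Baseline to a Day 1 predose ECG that is not scheduled; separately, the QTcF categories are based on triplicates although ECGs are single

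*SAP*

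**What the plan says.** **Baseline in the SAP.** Section 5.1.1.6 opens with a general rule: "Unless otherwise stated, a Baseline value refers to the last non-missing value collected prior to the first treatment". Table 5 then gives rules by procedure. For vital signs it reads "Predose on Day 1 or if missing then the Baseline data will be missing". The next row, single 12-lead ECG, shows no text of its own. Laboratory tests have a separate entry: Day -1, or failing that the most recent earlier value.

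**ECG timing in the protocol.** The Schedule of Activities (Section 1.3) places the ECG at Screening, Day -1, Day 6, Day 11, Day 15 and SFU/ETV. Vital signs are placed at those visits and also on Day 1. Footnote c states: "Clinical assessments performed on Days 1, 6, and 11 need to be performed predose".

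**ECG Baseline in the protocol.** Section 7.1.2 refers to "Change from Baseline (Day -1, before first treatment, Day 6, and Day 11) of QTcF >60ms". Section 9.2.4.1 plans summaries of "changes from Baseline (Day -1, before first treatment, Day 6, and Day 11) through treatment periods". SAP Appendix 4 (Section 6.4) declares no change from the protocol-planned analyses.

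**Replication.** Footnote f of the Schedule says "12-lead ECG will be performed in single after a rest in supine position for at least 10 minutes before recordings", with triplicates only if clinically indicated. Section 8.3.3 agrees, and Section 9.2.4.1 adds "The single 12-lead ECG will be recorded as timepoints defined in schedule of activities". SAP 5.5.3.3.1 nevertheless defines the QTcF categories, observed and change from Baseline, on the average of triplicate recordings.

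**The concern.** There are three separate points.

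1. If Table 5 applies the vital-sign rule to ECG, it names an assessment the protocol does not schedule and forbids any substitute. The general rule cannot rescue it, because that rule yields wherever something else is stated. ECG changes from Baseline, including the QTcF change categories (<30, 30 to <60, >=60 msec), would then be missing throughout.
2. On either reading, the SAP uses one study-level Baseline before first treatment, while the protocol's wording also names Day 6 and Day 11. A change measured from Day 6 or Day 11 is a different quantity from one measured from Day -1, and no difference is recorded.
3. The QTcF categories call for a triplicate mean that will normally not exist. When a triplicate is taken, the SAP's rules for using it disagree.

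At stake are the exploratory ECG summaries. If the gap were noticed only when output came back empty, the Baseline would be chosen after data had been seen in an open-label study.

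**Working it through.** The plan states no figure for this point that could be reproduced. The check compares the texts and counts.

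**Step 1: how to read the blank ECG cell.** SAP Table 7 uses the same layout. Vital Signs and ECG are blank beneath the laboratory entry, which is by time point and sequence; Sections 5.5.3.2.1 and 5.5.3.3.1 confirm that they take that entry. Medical history and concomitant medications are blank beneath the by-sequence entry for disposition; Sections 6.1.3 and 6.1.5 confirm that they take it. By the SAP's own convention a blank means the entry above, which for ECG in Table 5 is the predose Day 1 rule.

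**Step 2: is there a Day 1 ECG?** Rows of the Schedule of Activities:

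| | Screening | D-1 | D1 | D2-5 | D6 | D7-10 | D11 | D12-14 | D15 | SFU |
|---|---|---|---|---|---|---|---|---|---|---|
| ECG (6 entries) | X | X | | | X | | X | | X | X |
| Vital signs (7 entries) | X | X | X | | X | | X | | X | X |

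The available text of this table is imperfect in at least two rows: the third dose sits under D12-14, and confinement is marked at Screening but not on Day -1. The entry counts alone show that the two rows differ by one, not where. That the missing entry is Day 1 rests on column position and on the wording of protocol 7.1.2 and 9.2.4.1, which name Day -1, Day 6 and Day 11 for ECG but not Day 1. For laboratory tests and vital signs, Section 9.2.4.1 does name Day 1.

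**Step 3: counts, with the 18 participants planned in SAP Section 3.**
- Scheduled ECGs after first dose: 18 x 4 (D6, D11, D15, SFU) = 72.
- Changes computable on the shared-cell reading: 0 of 72, barring an unscheduled predose Day 1 ECG.
- Changes computable on the blank-cell reading, or with an explicit Day -1 entry: up to 72 of 72.
- All scheduled ECGs: 18 x 6 = 108, of which 0 are planned as triplicates.

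**Step 4: what the summaries could show even when computed.** Time since the preceding dose:
- D6 and D11 (predose): 5 x 24 = 120 h
- D15: 4 x 24 = 96 h
- SFU, 5 to 9 days after the last dose: 120 to 216 h

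Protocol 4.2 gives half-lives for minzasolmin and its two metabolites that "are 11, 10 and 16 hours, respectively". The fraction left after 96 h is 2^(-96/half-life):
- 11 h: 2^(-8.7) = 0.0024, or 0.24%
- 10 h: 2^(-9.6) = 0.0013, or 0.13%
- 16 h: 2^(-6) = 0.0156, or 1.6%

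Protocol 2.2 gives 11 to 13 h for the parent. At 13 h the figure is 2^(-7.4) = 0.006, or 0.6%. The scheduled ECGs could therefore show little acute drug effect; only an early-termination ECG might fall sooner after a dose.

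**Step 5: triplicates.** In the SAP, planned triplicates belong to vital signs (Section 5.5.3.2, matching protocol 8.3.2). Each scheduled ECG yields one QTcF value, so the intended input can be inferred. For a clinically indicated triplicate after dosing, three rules compete: Section 5.5.3.3.1 takes the mean for the categories; Section 5.1.1.7 keeps only the first reading for descriptive statistics; Section 5.1 takes the reading closest to the intended time, or the later one if two are equidistant.

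**The case against.** The case against has real points.

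- **Table 5 may simply have an empty ECG cell.** Nothing confirms the shared entry for ECG Baseline specifically, and Table 7 repeats an identical entry in two adjacent rows, so its layout is not a strict convention. If the cell is empty, the general rule gives Day -1 and the first point reduces to adding an explicit entry. This stands as a limit on certainty.
- **The protocol's ECG Baseline wording is ambiguous.** The phrase about first treatment could be a time point separate from Day -1. That is so, but it does not put a Day 1 ECG into the Schedule.
- **An unscheduled predose Day 1 ECG would count as Baseline.** Section 5.1.1.6 allows this, so the zero refers to scheduled assessments only.
- **A single Baseline may be permissible refinement.** Protocol Section 9 says the SAP will be more detailed, and the protocol does not say whether Day 6 and Day 11 are period-specific Baselines. This weakens the second point to a need for clarification.
- **Triplicates can exist.** Protocol 7.1.2 calls for them when an abnormality is considered clinically significant, and a specific QTcF rule would ordinarily override a general one. This stands, but it covers exceptional recordings; the SAP applies the triplicate mean to all of them.

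**Conclusion.** The concern holds and is minor. On the most likely reading of Table 5, 0 of 72 scheduled ECG changes from Baseline are computable; on the alternative reading up to 72 are. That range rests on 18 participants with complete visits, on no unscheduled predose Day 1 ECG, and on the Schedule's ECG row being correctly placed. Confidence in the Baseline part is therefore medium. The triplicate mismatch does not depend on Table 5 and is contradicted by that table's own row label.

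The primary PK analysis, observed ECG summaries, listings and the protocol's QTcF withdrawal criterion are unaffected. The failure would be visible as empty output, and the scheduled ECGs come too late after dosing to reveal much acute effect in any case.

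**What to change.** 1. In SAP Table 5, give ECG its own entry: the last non-missing ECG before first dose, scheduled on Day -1.
2. State whether Day 6 and Day 11 serve as Baselines in the ECG summaries. Align Table 5 with protocol 9.2.4.1, or record the difference in Appendix 4.
3. In SAP 5.5.3.3.1, base the QTcF categories on the scheduled single ECG. Add one line on how a clinically indicated triplicate is used, and say that it takes precedence over Sections 5.1 and 5.1.1.7.

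These changes concern the analysis only. They cost a few lines of SAP wording and need no new data or visits.

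### SAP Table 5 gives vital signs a Day 1 predose baseline with no fallback, so a missed Day 1 set would leave a valid Day -1 reading unused

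*SAP*

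**What the plan says.** SAP 5.1.1.6 opens with a default: "Unless otherwise stated, a Baseline value refers to the last non-missing value collected prior to the first treatment". Under that default both scheduled and unscheduled readings qualify.

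Table 5 in the same section then sets rules by procedure. For vital signs the entry is "Predose on Day 1 or if missing then the Baseline data will be missing". For laboratory tests baseline is the Day -1 value, and "If this value is missing, the most recent value obtained prior to Day 1 will be used as Baseline".

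Protocol 9.2.4.1 describes the planned summaries as "Vital sign variables (SBP, DBP, PR, respiration rate, and body temperature) and changes from Baseline (Day -1, or Day 1 before first treatment". The Schedule of Activities (protocol 1.3) marks vital signs at Screening, Day -1, Day 1, Day 6, Day 11, Day 15 and SFU/ETV. Its footnote c adds: "Clinical assessments performed on Days 1, 6, and 11 need to be performed predose".

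SAP 5.5.3.2.1 summarizes vital signs and their changes from baseline descriptively, by time point and sequence. SAP 6.4 lists no change to the protocol-planned analyses.

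**The concern.** The protocol allows two baseline days for vital signs, and both are scheduled for every participant. Table 5 keeps one of them and rules out using the other when the first is missing. No reason is given, and the laboratory row a few lines below does the opposite.

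At stake is a participant who has a valid pre-treatment reading on Day -1, misses the Day 1 predose set, and then drops out of every vital-sign change table. In a study of 18, tabulated over six sequences, a single such participant is visible in the output.

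**Working it through.** The plan gives no figure on this point, so there is none to reproduce. The check compares the texts, then sizes the loss.

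**1. The texts side by side**

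| Source | Vital-sign baseline | If Day 1 predose is missing |
|---|---|---|
| Protocol 9.2.4.1 | Day -1, or Day 1 before first treatment | Day -1 is an accepted baseline day; no order or fallback is spelled out |
| SAP 5.1.1.6, default | Last non-missing value before first treatment | Day -1 would be used |
| SAP Table 5, vital-sign row | Day 1 predose | Baseline is missing |
| SAP Table 5, laboratory row (for comparison) | Day -1 | Not relevant; a missing Day -1 value is replaced by the most recent earlier one |

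**2. Loss for one affected participant**

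Post-baseline time points in the Schedule of Activities: Day 6, Day 11, Day 15 and SFU, so 4. Variables in SAP 5.5.3.2: pulse rate, systolic and diastolic blood pressure, respiratory rate and body temperature, so 5.

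- Change values lost: 4 x 5 = 20.
- Planned for 18 completers: 20 x 18 = 360.
- Share lost: 20/360 = 5.6%.

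If only one variable is missing on Day 1, the loss is 4 of the 4 x 18 = 72 change values for that variable, again 5.6%.

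**3. Loss within a table cell**

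With 18 participants over 6 sequences and equal allocation (assumed), each cell holds 18/6 = 3. One missing baseline leaves 2, a loss of one third of that sequence's change data at every post-baseline time point. This follows the SAP's layout by sequence; protocol 9.2.4.1 speaks of presentation by treatment group, where the fraction would differ.

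**4. How often it might happen**

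The documents give no rate. Let p be the chance that a participant's Day 1 predose set is missing, with 1% to 10% assumed purely for illustration.

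- Expected participants without a baseline under Table 5: 18p.
- Chance that at least one is affected: 1 - (1 - p)^18.
- Expected number with a Day -1 fallback, taking the same p for Day -1 and independence: 18p².

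| p | 18p | At least one of 18 affected | 18p² |
|---|---|---|---|
| 1% | 0.18 | 16.5% | 0.002 |
| 2% | 0.36 | 30.5% | 0.007 |
| 5% | 0.90 | 60.3% | 0.045 |
| 10% | 1.80 | 85.0% | 0.18 |

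If p is zero, both rules give the same tables.

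**The case against.** The case for leaving Table 5 alone has four parts.

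- **The exception is permitted.** The general rule yields to anything stated otherwise, and Table 5 states otherwise. Day 1 predose is also one of the two days the protocol allows. This stands: the SAP has made a narrower choice, not an error of logic.
- **A missed set is unlikely.** Participants are resident during the treatment periods, Day 1 assessments are required predose, and under SAP 5.1.1.7 a repeat or unscheduled reading before first dose can serve as baseline. This stands too, and it is why the expected loss is small.
- **The lost values matter little.** They are exploratory and descriptive, and the observed readings stay in the tables and listings. The Day 6 and Day 11 readings are predose, 5 days (120 hours) after the previous dose, and Day 15 is 4 days (96 hours) after the last. With the 11-hour half-life in protocol 4.2 these are 120/11 = 10.9 and 96/11 = 8.7 half-lives, so the change values say little about acute drug effect. This limits the weight of the point.
- **A single baseline day keeps like with like.** Days 1, 6 and 11 share predose, dosing-day conditions, and a fallback would mix baseline days within a table. This is a reasonable preference, but it does not defeat the change. The protocol itself accepts Day -1, Day 1 predose would remain first choice, and Day -1 would enter only where there is otherwise no baseline. The SAP's general policy against imputing missing data is no bar either, since Day -1 is a measured value.

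**Conclusion.** The point holds as a minor one. Table 5 narrows the protocol's vital-sign baseline to one day and sets it to missing if that day's reading is absent, although a second protocol-accepted reading is scheduled. If, and only if, a Day 1 predose set is missed, the participant loses 20 of 360 change values (5.6%), or about one third of a sequence-level cell under equal allocation. The frequency is unknown; the 1% to 10% range is an assumption. Primary PK and secondary TEAE endpoints are unaffected.

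A reader might infer more than the documents support:

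- *That the protocol makes Day -1 the vital-sign baseline.* It names Day -1 or Day 1 before first treatment and sets no order between them.
- *That the SAP contradicts itself.* The default is explicitly subject to exceptions, and Table 5 is one.
- *That SAP 6.4 is a misdeclaration.* Choosing one of two allowed days is arguably within the protocol. At most, the narrowing would have been worth a sentence there.
- *That data will be discarded.* Nothing is lost while the Day 1 set is complete.

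**What to change.** In SAP Table 5, for the vital-sign row only, replace the present rule with: *Predose on Day 1; if missing, the last non-missing value before first treatment (normally Day -1).* A listing flag for any participant whose baseline is not from Day 1 would deal with the concern about mixed baseline days.

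This agrees with the SAP's own default and stays within the days the protocol accepts. It does add an order of preference that the protocol leaves open. The cost is one line of SAP text and the matching derivation; results do not change when Day 1 data are complete.

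The ECG baseline should have its own entry. In the public text the ECG row of Table 5 shows no rule of its own, and it cannot be settled whether it shares the vital-sign cell. The Schedule of Activities has no ECG on Day 1, and protocol 9.2.4.1 describes ECG "changes from Baseline (Day -1, before first treatment, Day 6, and Day 11) through treatment periods". The revised vital-sign wording should therefore not be carried over to ECG by default.
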